9.2 Analysis Data Definitions

9.2.1 Baseline Definition

Unless otherwise stated, baseline for post-dose evaluations is defined as the last observation recorded before the first study drug administration. The last observation can be an unscheduled / repeated measurement.

For PK, vital signs and ECG in the core phase a second baseline is defined as the last non-missing measurement taken before dosing on Day 10 for treatment part A and on Day 7 for treatment part B, i.e. the first coadministration.

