8.2.3 Vital Signs

Supine blood pressure, supine pulse rate, respiratory rate, and body temperature will be assessed at the times indicated in the Schedule of Assessments in [Appendix 1](#). Vital signs may also be performed at other times if judged to be clinically appropriate or if the ongoing review of the data suggests a more detailed assessment of vital signs is required.

All measurements will be performed singly and repeated once if outside the relevant clinical reference range.

Patients must be supine for at least 5 minutes before blood pressure, heart rate, and temperature measurements. During the in-house period of the Core Phase, blood pressure, heart rate, and temperature measurements should be conducted in the morning. When scheduled at the same time, vital sign assessments are to be performed prior to PK blood draws, with blood draws to occur as close to the nominal times as possible except for Screening and Day -1.

8.2.4 12-Lead Electrocardiogram

Resting 12-lead ECGs will be recorded after the patient has been supine and at rest for at least 5 minutes at the times indicated in the Schedule of Assessments in [Appendix 1](#).

Single 12-lead ECGs will be repeated once if either of the following criteria apply postdose:

- QTcF > 500 msec
- QTcF change from the baseline (predose) is > 60 msec

Additional 12-lead ECGs may be performed at other times if judged to be clinically appropriate or if the ongoing review of the data suggests a more detailed assessment of ECGs is required. The investigator (or designee) will perform a clinical assessment of each 12-lead ECG. When numerous assessments are scheduled at the same time, ECGs are to be performed prior to vital sign assessments and PK blood draws, with PK blood draws to occur as close to the nominal times as possible except for Screening and Day -1.

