9.1.5 Unscheduled Measurements

Unscheduled measurements will be included in the listings. With the exception of unscheduled measurements used to define baseline or to define the largest change of CTCAE grade in shift table, unscheduled measurements will be excluded from the descriptive statistics and statistical analysis.

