18.1.4 Vital Signs

Descriptive statistics will be provided to summarize vital signs and changes from baseline at each scheduled time and presented separately for each treatment group. All Vital Signs, including repeats in response to abnormalities, will be listed.

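### An out-of-range vital sign is replaced by its repeat at baseline but, on the natural reading of the SAP, not after dosing, so mean changes from baseline can shift with no drug effect

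*SAP*

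**What the plan says.** Four provisions bear on this.

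- **When a repeat is taken.** Protocol 8.2.3: "All measurements will be performed singly and repeated once if outside the relevant clinical reference range". The rule is not limited to pre-dose or post-dose times, and it is triggered by the value itself.
- **Which reading is baseline.** SAP 9.2.1: "baseline for post-dose evaluations is defined as the last observation recorded before the first study drug administration", followed by "The last observation can be an unscheduled / repeated measurement". For the co-administration period, "a second baseline is defined as the last non-missing measurement taken before dosing on Day 10 for treatment part A", with Day 7 as the counterpart in Part B. A repeat is the later of the two pre-dose readings, so it is selected in both cases.
- **What enters the summaries.** SAP 9.1.5: "unscheduled measurements will be excluded from the descriptive statistics and statistical analysis". That sentence opens with a carve-out, "With the exception of unscheduled measurements used to define baseline", and also exempts readings that set the largest CTCAE grade change in shift tables.
- **What is reported.** SAP 18.1.4: "Descriptive statistics will be provided to summarize vital signs and changes from baseline at each scheduled time". Repeats are named only for the listings: "All Vital Signs, including repeats in response to abnormalities, will be listed". SAP 9.2.3 defines change as the post-dose value minus baseline.

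**The concern.** A reading that triggers a repeat because it is extreme tends to be followed by a less extreme one, whatever the drug does. Using the repeat at baseline removes part of that chance extremity. Leaving the first reading in place after dosing does not. The two sides of the difference are then measured by different rules.

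As an illustration, take a first systolic reading of 150 and a repeat of 136. Before dosing, that pair gives 136. The same pair after dosing gives 150. The calculated change is +14 mmHg with nothing having happened.

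The same baseline is subtracted at 1, 2, 4 and 24 hours post-dose. For a given vital sign and population, the expected shift is therefore the same at each of those times, and adding patients does not reduce it. What is at stake is the descriptive mean change from baseline in the pamiparib-only and combination columns, in a study with a secondary objective on the safety and tolerability of the combinations.

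**Working it through.** The documents give no figure on this point to reproduce. They also give no reference ranges, SDs or correlations for vital signs, so every size below rests on assumed inputs.

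**Model with no drug effect.** Each reading has mean m and total SD s. The repeat correlates r with the first reading, and the reference range is L to U. Baseline is the first reading if it lies in range, otherwise the repeat. Post-dose is the scheduled reading.

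**Formula.** Given a first reading X, the repeat has expectation m + r(X − m). Replacing X by its repeat therefore moves baseline by −(1 − r)(X − m) on average, and only when X is out of range. Under a normal distribution, the out-of-range parts of X − m contribute s·φ((U − m)/s) from above and −s·φ((m − L)/s) from below, where φ is the standard normal density. The scheduled post-dose reading has mean m. Hence

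expected change = (1 − r) · s · [φ((U − m)/s) − φ((m − L)/s)].

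**One case in full.** Assume systolic range 90-140, mean 130, between-patient SD 14 and within-patient SD 8.

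- s = √(14² + 8²) = √260 = 16.1
- r = 196/260 = 0.75, and (1 − r)·s = 64/16.1 = 3.97
- φ(10/16.1) − φ(40/16.1) = 0.329 − 0.018 = 0.311
- expected change = 3.97 × 0.311 = **+1.23 mmHg**, with 27% of baselines replaced

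**Range over the assumed inputs** (systolic, 90-140, between-patient SD 14; 2,000,000 simulated patients per cell; mean change in mmHg):

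| Mean | Within-patient SD 6 | SD 8 | SD 10 |
|---|---|---|---|
| 120 | +0.26 | +0.45 | +0.67 |
| 130 | +0.73 | +1.23 | +1.80 |
| 135 | +0.88 | +1.48 | +2.15 |

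**Sign.** The formula is zero when m is the midpoint of the range, which is 115 mmHg here, and changes sign there. With s = 15 and r = 0.6 it gives 0.00 at mean 115, −1.29 mmHg at 105 and +1.85 mmHg at 130. For pulse (assumed range 60-100, s = 12, r = 0.6) it gives −1.04 bpm at mean 72 and +1.04 bpm at mean 88.

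**Sensitivity to r.** The shift is proportional to 1 − r. Keeping mean 130 and s = 16.1:

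- r = 0.90: 0.10 × 16.1 × 0.311 = +0.50 mmHg
- r = 0.95: 0.05 × 16.1 × 0.311 = +0.25 mmHg

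**Against sampling error.** With s = 15 and r = 0.6, the standard error of the mean systolic change at n = 12 is about 3.7-3.8 mmHg. For means of 120 to 140 the shift is +0.66 to +2.38 mmHg, that is 0.66/3.74 = 0.2 to 2.38/3.81 = 0.6 standard errors.

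**After the fix.** With the scheduled reading on both sides, both expectations equal m and the expected change is zero. Simulated means at r = 0.6 were within 0.03 units of zero in every setting.

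**The case against.** The strongest objection is textual. SAP 9.1.5 excludes *unscheduled* measurements and does not mention repeats. An out-of-range repeat is required by the protocol at a scheduled time, so a programmer might treat it as part of that visit. A reader might infer that the SAP expressly discards post-dose repeats, and it does not say that in terms. The exclusion is still the natural reading: SAP 9.2.1 pairs *unscheduled* with *repeated*, SAP 9.1.5 makes a specific exception for baseline, and SAP 18.1.4 mentions repeats only for listings. If something else was intended, the SAP needs to say so.

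Several stronger inferences are tempting but not supported:

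- **A uniform upward bias.** The direction depends on where values sit in the range, and it can differ between vital signs or be nil.
- **Every treatment column affected.** The schedules place no vital signs in the rifampin-only period (Days 3-9) or the itraconazole-only period (Days 3-6).
- **A named endpoint compromised.** The secondary endpoint is vital sign assessments. Change from baseline is one planned summary of it, and the post-dose observed values do not depend on the baseline rule.
- **The combination-versus-alone contrast distorted.** If each period uses its own pre-dose baseline, the shift is similar in both and largely cancels.
- **Core Phase ECGs affected in the same way.** The repeat criteria in Protocol 8.2.4 apply post-dose, so this route does not carry over.

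It is also fair to say that the size rests wholly on assumed inputs, that a repeat may correlate more closely with the first reading than assumed, and that no formal testing is planned (SAP 9.4.3). Repeats are listed, and clinically significant abnormalities are recorded as adverse events (Protocol 9.1.5). These points stand and limit the severity. They do not remove the inconsistency.

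**Conclusion.** The concern holds as a minor point. On the natural reading of SAP 9.1.5, the plan corrects for regression to the mean at baseline but not after dosing, so Core Phase mean changes in vital signs in the pamiparib-only and combination columns can be shifted with no drug effect. Under the stated systolic assumptions the shift is about +0.3 to +2.2 mmHg. It is smaller if the repeat tracks the first reading more closely, zero at a mean of 115 mmHg and negative below that. It is modest beside the standard error at n = 12 and leaves the PK analysis untouched. It merits correction because it is systematic and is removed by a rule that costs almost nothing.

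**What to change.** In SAP 9.2.1, define both vital-sign baselines (before first dose, and before dosing on Day 10 in Part A or Day 7 in Part B) as the scheduled pre-dose reading, with a repeat used only if that reading is missing or invalid. In SAP 9.1.5, state that repeats taken because a vital sign is out of range count as unscheduled, so that the scheduled reading is summarised before and after dosing and all repeats are listed.

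Using the repeat on both sides would also remove the shift in the mean. It is not the better choice, because replacing first readings after dosing could mask transient abnormal values in a safety summary.

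The cost is a short wording change in each of two SAP sections, with no new data or procedures. The small downside is that a chance-extreme first reading stays in an individual patient's baseline.

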9.2.2 Treatment/Patient Grouping

Treatment emergent Adverse events (TEAEs) will be summarized by the last treatment received, i.e. "Treatment at onset"

The following treatment labels will be used for the core phase:

Part/Treatment Arm	Treatment Label	Dosing	Used for assessments done at
A	'Pamiparib only'	60 mg single dose	Day 1 - 2
A	'Rifampin'	600 mg QD	Day 3 - 9
A	'Pamiparib with Rifampin'	60 mg and 600 mg	Day 10 - 12
B	'Pamiparib only'	20 mg single dose	Day 1 - 2
B	'Itraconazole'	200 mg QD	Day 3 - 6
B	'Pamiparib with Itraconazole'	20 mg and 200 mg	Day 7 - 9

9.2.3 Other Definitions

General definitions for variables as used in the text.

Change from baseline will be calculated for safety measures, see below.

Variable	Dataset	Definition/Calculation
Change from Baseline	All	Post-dose Observation minus Baseline Observation
Study Day (Prior to first dose day)	All	Date of Measurement minus Dose Date
Study Day (Predose on first dose day and post first dose)	All	Date of Measurement minus Dose Date +1
TEAE	AE	AE is a TEAE if the AE with an onset date on or after the date of first dose of study medication until the date of last study medication dose plus 30 days.

9.2.4 ADaM Datasets

The analysis datasets will be generated in accordance with Clinical Data Interchange Standard Consortium (CDISC) Analysis Data Model (ADaM) Version 2.1.

ADaM compliant datasets will be delivered to the sponsor. A define.xml file version 2 with the corresponding metadata will be included. Analysis results metadata are excluded.

9.3 Software

The statistical analysis and reporting will be done using SAS® for Windows™ version 9.4 or higher (SAS Institute, Inc.).

PK parameter calculations will primarily be done using Phoenix® WinNonlin® version 8.1 or higher (Certara, Inc.).

PK computations or summaries may also be performed in SAS®.

9.4 Statistical Methods

9.4.1 Statistical Outlier Determination

No statistical outlier analysis is planned.

9.4.2 Predetermined Covariates and Prognostic Factors

There are no predetermined covariates or prognostic factors.

9.4.3 Hypothesis Testing

No formal hypothesis testing will be done.

9.5 TFL Layout

Report layout will be according to the PRA EDS – ICH E3 compliant – CSR Template. The layout of Tables, Figures and Listings (TFLs) will be according to the PRA EDS standards.

10.0 Analysis Sets

10.1 Safety Population

The safety population will include all patients who received at least 1 dose of pamiparib.

10.2 Pharmacokinetic Population

The PK population will include all patients who received at least 1 dose of pamiparib and have evaluable PK data. A patient will be excluded from the PK summary statistics and statistical analysis if the patient has an AE of vomiting that occurs at or before 2 x median t_{max} .

Analyses	Safety Population	Pharmacokinetic Population
Disposition Summaries	✓	
Safety Assessments	✓	
Baseline Characteristics	✓	
Primary Endpoint		✓
Secondary Endpoint	✓	

11.0 Patient Disposition

Patient disposition will be summarized by part using frequency counts and the corresponding percentages. The number of patients in each analysis population, number of patients discontinued, the primary reason for treatment discontinuation, and the primary reason for study discontinuation will be summarized.

Disposition data including date of informed consent and end of treatment will be listed.

12.0 Protocol Deviations and Violations

Protocol deviations/violations will be listed.

13.0 Demographic and Baseline Characteristics

13.1 Demographics

Patient demographics will be summarized descriptively for all patients by part. The summary will include the patients' age at informed consent (in years), gender, race, ethnicity, weight (in kg) at baseline, height (in cm), and BMI (in kg/m²) at baseline. Demographics will be summarized for the safety analysis set.

Associated person's demographics will be listed.

13.2 Medical History

Medical history will be listed by part.

Disease history will be listed by part.

13.3 Anti-Cancer Treatments and Procedures

The following listings will be provided:

- listing of previous anti-cancer therapy
- listing of previous anti-cancer radiotherapy
- listing of post treatment discontinuation anti-cancer therapy

These will include all collected data from the corresponding CRF pages.

13.4 Other Baseline Characteristics

The following baseline characteristics will be listed:

- Non-compliance to inclusion or exclusion criteria (if any)
- The results of alcohol screen
- The results of urine drug screen
- The results of HBV/HCV tests
- Viral load assessments

14.0 Prior and Concomitant Medications/Procedures

Prior and concomitant medication and procedures will be listed by part. Medications with an end date prior to the first dose of study drug will be considered prior medications. If a partial date allows a medication to be considered concomitant it will be categorized as such.

15.0 Treatment Compliance and Exposure

Exposure data will be listed.

The number of patients receiving doses of pamiparib, rifampin or itraconazole will be summarized separately for the core phase.

The following variables will be summarized using extension phase data only:

- The number of cycles initiated
- Duration of treatment

- Dose intensity (see below)
- Number of patients with exactly one planned dose reduction and the number of patients with 2 or more planned dose reductions.

The duration of treatment will be calculated as the number of days from the first dose of study drug to the day of the last dose of study drug +1. If a patient is ongoing, then the date of the data cutoff will be used.

Dose intensity will be calculated for each patient by adding the actual total dose received divided by the duration of treatment. Relative dose intensity is defined as total actual dose received divided by total planned dose. Both will be shown.

16.0 Pharmacokinetic Analyses

16.1 Pharmacokinetic Variables

- Plasma concentration of pamiparib with and without rifampin and itraconazole, respectively.
- PK Parameters for pamiparib with and without rifampin and itraconazole, respectively

16.2 Estimation of Pharmacokinetic Parameters

Patients who experience events that may affect their PK profile (e.g. lack of compliance with dosing) may be excluded from the PK analysis. At the discretion of the pharmacokineticist, a concentration value may also be excluded if the deviation of sampling time from the nominal time is of sufficient concern or if the concentration is anomalous for any other reason.

The following PK parameters will be calculated as data allows for pamiparib concentrations in plasma:

Primary:

Parameter	Description	SAS Programming Notes
C _{max}	Maximum plasma concentration. Observed peak analyte concentration obtained directly from the experimental data without interpolation, expressed in concentration units	C _{max} from WNL
AUC _{last}	Area under the concentration-time curve (time 0 to time of last quantifiable concentration).	AUC _{last} from WNL
AUC _{0-12h}	Area under the concentration-time curve (time 0 to time 12h) as observed.	AUC at tpt=12 h from WNL
AUC _{0-9h}	Area under the concentration-time curve (time 0 to time 9h) as observed.	AUC at tpt=9 h from WNL
AUC _{inf}	Area under the plasma concentration-time curve (time 0 to infinity). Percent extrapolation less than or equal to 20% and an r ² greater than 0.90 are required to retain AUC _{inf} .	AUCINF_obs from WNL If AUC_%Extrap_obs >20% or Rsq ≤ .90 then parameter is deleted
T _{max}	Time to maximum plasma concentration. First observed time to reach peak analyte concentration obtained directly from the experimental data without interpolation, expressed in time units.	T _{max} from WNL

Parameter	Description	SAS Programming Notes
T _{1/2}	Terminal phase half-life expressed in time units. Percent extrapolation less than or equal to 20% and r ² greater than 0.90 is required to retain T _{1/2} .	HL_Lambda_z from WNL If AUC_%Extrap_obs >20% or Rsq ≤ .90 then parameter is deleted
CL/F	Apparent clearance Percent extrapolation less than or equal to 20% and r ² greater than 0.90 is required to retain T _{1/2} .	CL_F_obs from WNL If AUC_%Extrap_obs >20% or Rsq ≤ .90 then parameter is deleted
V _z /F	Apparent volume of distribution during terminal phase Percent extrapolation less than or equal to 20% and r ² greater than 0.90 is required to retain T _{1/2} .	Vz_F_obs from WNL If AUC_%Extrap_obs >20% or Rsq ≤ .90 then parameter is deleted

Note: AUCs are calculated using linear up / log down, expressed in units of concentration x time.

Additional PK parameters (only in listings):

Parameter	Description	SAS Programming Notes
AUC _{extrap %}	Percentage of AUC _{inf} obtained by forward extrapolation.	AUC_%Extrap_obs from WNL
r ²	Goodness of fit statistic for the terminal phase rate constant (k _{el})	Rsq from WNL
k _{el}	Rate constant for terminal phase	Lambda_z from WNL If AUC_%Extrap_obs >20% or Rsq ≤ .90 then parameter is deleted
k _{el} , t(lo)	First time point value used in the calculation of k _{el}	Lambda_z_lower from WNL If AUC_%Extrap_obs >20% or Rsq ≤ .90 then parameter is deleted
k _{el} , t(hi)	Last time point value used in the calculation of k _{el}	Lambda_z_upper from WNL If AUC_%Extrap_obs >20% or Rsq ≤ .90 then parameter is deleted
k _{el} , t(n)	Number of time points used in the calculation of k _{el}	No_points_lambda_z from WNL If AUC_%Extrap_obs >20% or Rsq ≤ .90 then parameter is deleted

The plasma PK parameters of pamiparib following pamiparib dosing on Days 1 and 10 in Part A and Days 1 and 7 in Part B will be calculated from pamiparib concentration-time profiles using standard noncompartmental methods, with WinNonlin®.

In estimating the PK parameters, BQL values at the beginning of the profile will be set to zero. BQL values that occur after the first quantifiable point will be set to missing. Values that are embedded between BQLs, or quantifiable values occurring after two or more BQLs, may be set to missing at the discretion of the pharmacokineticist. Actual sampling times, rather than scheduled sampling times, will be used in all computations involving sampling times. If the actual time or dose time is missing, the scheduled time may be substituted in order to calculate the PK parameter. In the event the PK draw occurs during the start or end of daylight savings time, the time will be adjusted to reflect the actual time from when the study drug was taken rather than the time on the clock.

As appropriate, additional PK parameters may be calculated and reported.

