1.2.1.1 Pharmacokinetics Data for BGB-290-AU-002

In the first-in-human Phase 1 study, interim pharmacokinetics (PK) data of pamiparib showed that pamiparib is rapidly absorbed and eliminated after oral administration. The maximum serum concentration and the drug exposure area under the concentration-time curve (AUC) increased in a nearly dose proportional manner from 2.5 to 120 mg twice a day both after the single-dose administration and at steady-state. The terminal half-life was determined to be approximately 13 hours, with a range of 5.5 to 34 hours. At steady-state, from 2.5 to 120 mg twice a day, drug exposure was increased in a dose-dependent manner.

A total of 13 patients in Study BGB-290-AU-002 contributed to serial plasma samples at predose, 0.5, 1, 2, 4, 7, 24 and 48 hours after a single 60 mg dose of pamiparib, either fasted or with high-fat breakfast, each followed by a 5-day washout for food-effect PK investigation.

[figure not shown]
When pamiparib was administered with food, a reduction of 15% in AUC and 41% in C_{max} was observed, along with a delay of T_{max} from 2 to 7 hours.

The 15% reduction in AUC is not considered to be clinically relevant and falls well within the variability of pamiparib exposure of approximately 50% coefficient of variation. Therefore, food restrictions are not required with pamiparib administration.

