16.4 Statistics of Pharmacokinetic Parameters

Statistical analyses will be performed to assess the effect of steady-state itraconazole and rifampin on the PK of pamiparib using the treatment in combination with pamiparib as test and the treatment with pamiparib only as reference.

Summary statistics will include number (N), arithmetic mean, standard deviation (SD), %CV, standard error of the mean (SEM), minimum, median, maximum, and geometric mean. For T_{\max} , only n, median, min and max will be presented.

Data for each treatment part will be analyzed separately.

A linear mixed model with a fixed effect for treatment and a random effect for patient will be used on the natural log-transformed parameters C_{\max} , $AUC_{0-\text{last}}$, and $AUC_{0-\text{inf}}$. A point estimate and the corresponding 90% CI for the difference between least squares means of Test and Reference treatment (Test – Reference) will be calculated. The antilogarithm of this value will be calculated to obtain the point estimate and the 90% CI for the ratio (Test/Reference) of the geometric means on the untransformed scale. For each

parameter selected for analysis, patients who do not have valid parameters in both periods will not be included for analysis.

The SAS PROC MIXED code is as follows:

```
proc mixed data = adpp;  
  by parameter;  
  class treatment patient;  
  model ln(aval) = treatment;  
  random patient;  
  lsmeans treatment / alpha = 0.1;  
  estimate "Pamiparib only vs Pamiparib with Itraconazole/Rifampin"  
  treatment -1 1 / e cl alpha=0.1;  
run;
```

For parameters C_{max} , AUC_{0-last} , and AUC_{0-inf} a listing of the individual patient ratios (Test/Reference) will be provided.

A forest plot of the geometric LS mean ratios of C_{max} , AUC_{0-last} , and AUC_{0-inf} will be provided for a visual representation of the data.

All plasma PK parameters will be listed by patient.

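### SAP 16.2 deletes AUCinf when extrapolation exceeds 20% or r-squared is 0.90 or less; if itraconazole slows clearance, Part B loses pairs selectively, and no pre-specified analysis uses the deleted values

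*SAP*

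**What the plan says.** The programming notes in SAP 16.2 for AUCinf, T1/2, CL/F and Vz/F read "If AUC_%Extrap_obs >20% or Rsq ≤ .90 then parameter is deleted", and the Description column makes the same limits a condition for keeping the value. The table of additional parameters repeats the rule for kel ("Lambda_z from WNL If AUC_%Extrap_obs >20% or Rsq ≤ .90 then parameter is deleted") and for its first time point, last time point and number of points. That makes eight parameters. Cmax, AUC0-last, AUC0-12, AUC0-9 and Tmax carry no such rule, and neither do the listed extrapolation percentage and r-squared.

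SAP 16.4 fits the mixed model to log Cmax, AUC0-last and AUCinf, separately by part. For each parameter, "patients who do not have valid parameters in both periods will not be included for analysis". The forest plot shows the same three ratios. SAP 9.1.2 rules out imputation unless otherwise noted. No sensitivity analysis is named.

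Three other statements soften the rule. SAP 16.4 says "All plasma PK parameters will be listed by patient". SAP 16.2 says "As appropriate, additional PK parameters may be calculated and reported". SAP 9.4.3 says "No formal hypothesis testing will be done".

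On the drug itself, Protocol 1.2.1.1 reports: "The terminal half-life was determined to be approximately 13 hours, with a range of 5.5 to 34 hours". The last PK sample is at 48 h (Protocol synopsis and Appendix 1).

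**The concern.** Part B exists to measure how far CYP3A inhibition raises pamiparib exposure. Protocol 1.3 names CYP3A as the main metabolic route, and Protocol 4.2 continues itraconazole for a day after the second pamiparib dose so that inhibition lasts through elimination. Slower elimination is therefore what the design looks for, and it is also what pushes a profile over the 20% limit. A patient with a long half-life or a large interaction is more likely to lose the Day 7 AUCinf, and with it the pair.

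At stake is one of the three modelled primary parameters. If the interaction is sizeable, the only planned AUCinf ratio could rest on few pairs, selected partly by the quantity being measured. Any analysis that restored the others would be post hoc and, under SAP 3.0, would have to be identified as unplanned in the study report.

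**Working it through.** **The plan's own figures.** 12 patients per part gives 2 × 12 = 24 enrolled, and 10 completers per part gives 20 (SAP 6.1). The size is expressly not power-based, so there is no assumed effect or variance to reproduce. The check below concerns the deletion rule and takes 10 pairs as the starting point.

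**Step 1: where the limit falls.** For a mono-exponential tail, the extrapolated share at 48 h is 2^(−48/t½). Setting this to 0.20 gives t½ = 48 × ln 2 / ln 5 = 20.7 h.

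| Half-life | Extrapolated | Source |
|---|---|---|
| 13 h | 7.7% | protocol, typical |
| 19.5 h | 18.2% | 13 h × 1.5 |
| 26 h | 27.8% | 13 h × 2 |
| 34 h | 37.6% | protocol, upper end |
| 68 h | 61.3% | 34 h × 2 |

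A 34-h patient fails on pamiparib alone. A 13-h patient fails after a rise of 20.7/13 = 1.6-fold, and a 5.5-h patient only after 20.7/5.5 = 3.8-fold.

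**Step 2: pairs kept and the retained ratio.** The documents give no expected itraconazole ratio, so the effect sizes are assumptions. The simulation used a one-compartment oral model, the protocol sampling times and linear-up/log-down AUC. The terminal slope had the best adjusted r-squared from at least 3 points after Cmax. The SAP rule and complete pairs were then applied. Also assumed: effect wholly on clearance; baseline half-life log-SD 0.4 within 5.5 to 34 h; 15% residual and 15% within-patient variation; 48-h sample quantifiable.

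| True ratio (log-SD of the effect) | Pairs kept of 10 | AUCinf, SAP rule | AUCinf, all estimable pairs | AUC0-last |
|---|---|---|---|---|
| 1.25 (0.1) | 6.7 | 1.22 | 1.25 | 1.17 |
| 1.5 (0.2) | 5.2 | 1.37 | 1.51 | 1.31 |
| 2 (0 to 0.3) | about 3 | 1.85 to 1.57 | 2.04 | 1.56 to 1.53 |

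Separate simulations under similar assumptions gave 1.35 to 1.39 at a true 1.5, and 1.60 to 1.90 at a true 2. About 15% of Day 1 values fail in any case, so with no interaction roughly 8 of 10 pairs remain.

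**Step 3: when the bias disappears.**
- Uniform effect, no noise: ratios of 1.25, 1.50 and 2.01, with 72%, 54% and 26% of pairs kept. Pairs are lost without bias.
- True 2 with half the log effect on bioavailability: 1.94 to 1.83, with nearly 6 of 10 pairs kept. With all of it on bioavailability: 2.00.
- Two-compartment model: 1.22, 1.39 to 1.40 and 1.65 to 1.80, so the pattern does not depend on a one-compartment tail.
- Part A, true 0.40: 0.40, with 85% of pairs kept.

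**Step 4: AUC0-last as a fallback.** For a 13-h patient with an f-fold effect, the 48-h ratio is f × (1 − 2^(−48/(13f))) / (1 − 2^(−48/13)). For f = 2 this is 2 × 0.722 / 0.923 = 1.56. It keeps its pairs but is also pulled toward 1.

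**Step 5: precision.** The 90% interval is the ratio ×/÷ exp(t × s × √(2/n)), where s is the within-patient log-SD and t the 95th percentile of Student's t with n − 1 degrees of freedom. For an assumed within-patient CV of 20% to 30%, the factor is 1.18 to 1.27 with 10 pairs, 1.31 to 1.49 with 5, and 1.60 to 2.01 with 3.

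**Step 6: carryover.** The pamiparib doses are 144 h apart, the last 96 h of that on itraconazole. For a 34-h patient whose half-life doubles, the residue at the Day 7 dose is 2^(−48/34) × 2^(−96/68) = 0.376 × 0.376 = 14% of the initial level, which raises that patient's AUCinf ratio by about 14%. On average carryover adds about 1% to 2% to the all-pairs ratio.

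**The case against.** The strongest reply is that the rule is a defensible quality criterion and that its harm is hypothetical. The documents give no itraconazole effect; at a true ratio of 1.25 the retained estimate is 1.22. Nothing is tested, so no pass/fail decision hangs on the ratio, and Cmax and AUC0-last are modelled without deletion. All of this stands, and it limits the weight of the point.

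A reader might infer that data are destroyed. They are not. AUC0-last and the extrapolation percentage stay listed, so AUCinf = AUC0-last / (1 − e), where e is the extrapolated fraction. SAP 16.3 lists every concentration and plots every profile, so slopes can be refitted; kel also follows as Clast × (1 − e) / (AUC0-last × e). Only the software's exact choice of points is not listed. What remains is that no planned analysis uses these values.

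A reader might also infer that the planned Part B result is biased or invalid. The documents do not support that: bias needs an effect on clearance of some size that varies between patients or occasions, or noise in the measurements, and none of these is specified.

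Finally, restored values are not a gold standard. Itraconazole stops on Day 8, 24 h after the second pamiparib dose, so a long extrapolated tail assumes that inhibition persists. Carryover falls mostly on the same long-half-life patients. This is a good reason to keep the 20% and 0.90 limits for the main ratio and to treat the wider analysis as supportive.

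**Conclusion.** The point holds as a cheap improvement of minor to moderate weight. The rule and the complete-pair restriction are explicit, and the 20.7-h cut-off follows from the 48-h sampling under a mono-exponential tail and lies inside the protocol's reported half-life range. The rest is conditional. If itraconazole acts through clearance, about half the Part B AUCinf pairs survive a 1.5-fold effect (retained ratio near 1.4) and about 3 of 10 survive a 2-fold effect (1.6 to 1.9). For a weak or uniform effect, or one on bioavailability, bias is small or absent. Part A is almost unaffected.

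These figures rest on assumed half-life spread and noise, on constant inhibition through the extrapolated tail, and on no Day 1 carryover. They show that selective loss is foreseeable. They do not predict the trial's result.

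**What to change.** In both tables of SAP 16.2, replace the instruction to delete with an instruction to flag, for all eight parameters. In the Description column for AUCinf, T1/2, CL/F and Vz/F, change the retention condition to a condition for inclusion in the main analysis and summary, so that the two columns agree. Keep 20% and 0.90 as the stated limits.

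Add to SAP 16.4:

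> The main AUCinf geometric mean ratio and the forest plot exclude flagged values. As a Part B sensitivity analysis, the same model will be fitted to all pairs with a terminal slope estimated from at least 3 points after Cmax in both periods, flagged or not, and repeated including values flagged for extrapolation only (r-squared above 0.90). Flagged individual ratios will be listed and marked. AUCinf, t1/2, CL/F and Vz/F will be summarized with and without flagged values, and the number flagged will be reported by day and reason. Day 7 predose concentrations will be reviewed for carryover when interpreting the sensitivity result.

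The complete-pair rule, the sampling schedule and the Cmax and AUC0-last analyses stay as they are.

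The cost is SAP wording, one sensitivity model fitted twice, and extra summary output. There is no protocol change and no additional sample. The downside is that the added values are noisier and some rest on heavy extrapolation: at a true ratio of 2, 4% to 6% of simulated Day 7 profiles exceed 60%. They also assume that inhibition lasts through the tail, so the result is supportive only.
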